3.3 EXPLORATORY OBJECTIVES

- To evaluate the magnitude, specificity and frequency of the H2-specific T-cell, B-cell responses and antibody responses at indicated time points throughout the study.

4. STUDY DESIGN AND METHODS

This is a Phase I, open-label, dose escalation study to evaluate the dose, safety, tolerability, and immunogenicity of the VRC-FLUNPF081-00-VP vaccine alone or in prime-boost regimens with the VRC-FLUDNA082-00-VP vaccine in healthy adults. The study schema is shown in **Table 2**. The hypotheses are that the vaccines are safe, well-tolerated, and will induce an antibody response to influenza virus subtype H2. The study will be conducted by the VRC Clinical Trials Program at a single site at the NIH Clinical Center (NIH CC).

Table 2: VRC 316 Vaccination Schema					
PART I: Dose Escalation of HA-F A/Sing					
Group	Dose Level	Age Cohorts	Subjects	Day 0 Prime	Week 16 (±4 weeks) Boost
1	Low dose	Ages 18-47	5	HA-F A/Sing, 20 mcg	
2	High dose	Ages 18-47	5	HA-F A/Sing, 60 mcg	HA-F A/Sing, 60 mcg
Total			10*	*Enrollment of up to 15 subjects is permitted if additional subjects are needed for safety or immunogenicity evaluations.	
				HA-F A/Sing injections are administered by needle and syringe.	
PART II: Evaluation of HA-F A/Sing and DNA A/Sing in Prime-Boost Regimens					
Group	Regimen	Age Cohorts	Subjects	Day 0 Prime	Week 16 (±4 weeks) Boost
3	DNA A/Sing HA-F A/Sing	Group 3A; 18-47	10	DNA A/Sing, 4 mg	HA-F A/Sing, 60 mcg
		Group 3B; 52-70	10		
4	HA-F A/Sing HA-F A/Sing	Group 4A; 18-47	10	HA-F A/Sing, 60 mcg	HA-F A/Sing, 60 mcg
		Group 4B; 52-70	10		
Total			40*	*Enrollment of up to 65 subjects is permitted if additional subjects are needed for safety or immunogenicity evaluations.	
				DNA A/Sing injections are administered by PharmaJet. HA-F A/Sing injections are administered by needle and syringe.	

4.1 STUDY POPULATION

All inclusion and exclusion criteria must be evaluated for eligibility.

4.1.1 Inclusion Criteria

A subject must meet all of the following criteria:

1. Healthy subjects aged 18-70 (excluding subjects born between 1966-1969)
2. Based on history and examination, must be in good general health and without history of any of the conditions listed in the exclusion criteria
3. Received at least one licensed influenza vaccine from 2014 to the present
4. Able and willing to complete the informed consent process
5. Available for clinic visits for 40 weeks after enrollment
6. Willing to have blood samples collected, stored indefinitely, and used for research purposes
7. Able to provide proof of identity to the satisfaction of the study clinician completing the enrollment process
8. Physical examination and laboratory results without clinically significant findings and a Body Mass Index (BMI) ≤ 40 within the 84 days before enrollment

Laboratory Criteria within 84 days before enrollment

9. White blood cells (WBC) and differential either within institutional normal range or accompanied by the site Principal Investigator (PI) or designee approval
10. Total lymphocyte count ≥ 800 cells/mm³
11. Platelets = 125,000 – 500,000/mm³
12. Hemoglobin within institutional normal range
13. Serum iron either within institutional normal range or accompanied by the site PI or designee approval
14. Alanine aminotransferase (ALT) ≤ 1.25 x institutional upper limit of normal (ULN)
15. Aspartate aminotransferase (AST) ≤ 1.25 x institutional ULN
16. Alkaline phosphatase (ALP) ≤ 1.1 x institutional ULN
17. Total bilirubin within institutional upper limit of normal (ULN)
18. Serum creatinine ≤ 1.1 x institutional ULN
19. Negative for HIV infection by an FDA approved method of detection

Criteria applicable to women of childbearing potential:

20. Negative beta-human chorionic gonadotropin (β -HCG) pregnancy test (urine or serum) on the day of enrollment
21. Agrees to use an effective means of birth control from at least 21 days prior to enrollment through the end of the study

4.1.2 Exclusion Criteria

A subject will be excluded if one or more of the following conditions apply:

1. Breast-feeding or planning to become pregnant during the study.

Subject has received any of the following substances:

2. More than 10 days of systemic immunosuppressive medications or cytotoxic medications within the 4 weeks prior to enrollment or any within the 14 days prior to enrollment
3. Blood products within 16 weeks prior to enrollment
4. Live attenuated vaccines within 4 weeks prior to enrollment
5. Inactivated vaccines within 2 weeks prior to enrollment.
6. Investigational research agents within 4 weeks prior to enrollment or planning to receive investigational products while on the study
7. Current allergy treatment with allergen immunotherapy with antigen injections, unless on maintenance schedule
8. Current anti-TB prophylaxis or therapy
9. Previous H2 influenza investigational vaccine
10. Receipt of a licensed influenza vaccine within 6 weeks before trial enrollment

Subject has a history of any of the following clinically significant conditions:

11. Serious reactions to vaccines that preclude receipt of study vaccinations as determined by the investigator
12. Hereditary angioedema, acquired angioedema, or idiopathic forms of angioedema
13. Asthma that is not well controlled
14. Diabetes mellitus (type I or II), with the exception of gestational diabetes
15. Thyroid disease that is not well controlled
16. Idiopathic urticaria within the past year
17. Evidence of autoimmune disease or immunodeficiency
18. Hypertension that is not well controlled
19. Bleeding disorder diagnosed by a doctor (e.g. factor deficiency, coagulopathy, or platelet disorder requiring special precautions) or significant bruising or bleeding difficulties with IM injections or blood draws
20. Malignancy that is active or history of malignancy that is likely to recur during the period of the study.
21. Seizure disorder other than 1) febrile seizures, 2) seizures secondary to alcohol withdrawal more than 3 years ago, or 3) seizures that have not required treatment within the last 3 years
22. Asplenia, functional asplenia or any condition resulting in the absence or removal of the spleen
23. Guillain-Barré Syndrome
24. Psychiatric condition that precludes compliance with the protocol; past or present psychoses; or within 5 years prior to enrollment, a history of suicide plan or attempt

25. Any medical, psychiatric, social condition, occupational reason or other responsibility that, in the judgment of the investigator, is a contraindication to protocol participation or impairs a subject's ability to give informed consent.

4.2 CLINICAL PROCEDURES AND EVALUATIONS

Evaluation of this vaccine will include laboratory tests, medical history, physical assessment by clinicians, and subject self-assessment recorded on a diary card for 7 days after each injection. Potential adverse reactions will be further evaluated prior to continuing the vaccination schedule. The schedule of study evaluations is described in this section and shown in table format in Appendix II. Total blood volume drawn from each subject will not exceed the NIH CC Guidelines.

4.2.1 Screening

Screening for this study will be completed through the VRC's screening protocol, VRC 500 (NIH 11-I-0164). Subjects will be recruited through Institutional Review Board (IRB)-approved advertising. The evaluations and sample collection that will be included in screening are a medical history, physical exam, any laboratory tests needed to confirm eligibility, and pregnancy test for females of reproductive potential.

If screening evaluations suggest a current concerning health condition or infection, such as hepatitis, then appropriate laboratory tests may be conducted to evaluate for these conditions. Additional assessments of health may be conducted at screening based on clinical judgment. Screening evaluations for specific eligibility criteria (Section 4.1) must be completed within the time interval specified prior to enrollment for the given parameter and may be repeated, as needed, to confirm eligibility. Research blood samples will be collected during screening; although generally collected in the 84 days prior to enrollment; a particular interval of time prior to enrollment for collection of these samples is not specified.

The informed consent form (ICF) will be reviewed and counseling related to pregnancy prevention will be provided.

Subjects who are not up to date on standard vaccinations may receive these, if available, during their participation in the screening protocol or at a later date during study participation. As part of the informed consent process, an Assessment of Understanding (AoU) is completed on the day the subject is scheduled to enroll prior to signing the VRC 316 protocol informed consent document. Incorrect answers will be explained to the volunteer, who will sign the ICF only after the study clinician is satisfied with the volunteer's understanding of the study.

4.2.2 Study Schedule

The Schedule of Evaluations in Appendix II provides details on the study schedule and the permitted visit windows. A clinician will discuss the target dates and timing of the study vaccination(s) and sample collections before completing an enrollment to help ensure that the subject can comply with the projected schedule.

The schedule of study visits, permitted windows for completing the visits, and evaluations performed at each visit are shown in Appendix II. After enrollment, deviations from the visit windows in completing study visits and study injections are discouraged and will be recorded as protocol deviations but are permitted at the discretion of the PI (or designee) in the interest of completing the vaccination schedule and obtaining subject safety and immunogenicity evaluations.

4.2.3 Enrollment and Randomization

Day 0 is defined as the day of protocol enrollment and first injection for all groups. Protocol-specific eligibility is reviewed on Day 0 as part of the enrollment process, but eligibility evaluations conducted during a screening visit are routinely used for eligibility if evaluations are within the specified window prior to Day 0. However, if clinical assessment on Day 0 suggests significant changes may have occurred since the screening visit, then evaluations done on Day 0 are used for eligibility. Day 0 evaluations and medical history prior to the first injection are the baseline for subsequent safety assessments.

Part I includes staged enrollment with required interim safety reviews before proceeding with the next dose group. In Group 1, five subjects will be enrolled with no more than one subject per day. Following dose escalation review, five subjects will be enrolled in Group 2 with no more than one subject per day. An internal safety review will determine whether enrollment can begin in Part II.

In Part II subjects will be stratified by age and randomized equally into Group 3 and Group 4. Neither the clinic staff nor the subjects will know in advance which group will be assigned to the enrollees in the study. The Protocol Statistician will prepare the randomization plan in advance and provide it to the site Pharmacy and Data Management Center.

The pharmacy database and study randomization will be set up prior to opening the study to accrual. The group assignment will become known to the staff and subject immediately after completing the electronic enrollment into the study on Day 0. The visit schedule is based on intervals of time after each study injection (Appendix II).

4.2.4 Administration of Study Vaccines

All study injections will be completed according to the assigned group and vaccines will be administered IM in the deltoid muscle. Blood draws must be completed before vaccinations.

On the injection day (prior to injection), study subjects will be clinically evaluated and samples will be collected as per Schedule of Evaluations (Appendix II). A subject who arrives at the clinic with fever or evidence of an acute illness that precludes administration of the vaccine may be rescheduled within the allowed study visit window.

Pregnancy test results for women of reproductive potential must be obtained on each injection day prior to the study injection and the results must be negative to proceed.

When choosing an arm for injection, clinicians should consider whether there is an arm injury, local skin problem or significant tattoo that precludes administering the injection or will interfere with evaluating the arm after injection.

Subjects enrolled in Group 1, Group 2, and Group 3 will be observed for a minimum of 1 hour. Vital signs (temperature, blood pressure, pulse and respiratory rate) will be collected at least 1 hour after the injection, prior to subject departure from the clinic. Subjects enrolled in Group 4 will be observed for a minimum of 30 minutes; vital signs will be collected after at least 30 minutes. The injection site will be inspected for evidence of local reaction.

Subjects randomized in Group 3 will receive the DNA A/Sing prime vaccine with the needle-free injection device, PharmaJet. The PharmaJet device requires that the DNA A/Sing product be administered as two 0.5 mL injections. When the PharmaJet device is used, subjects and clinicians will be asked to wear safety glasses during product administration. (See Section 8.5.2)

In keeping with the NIH CC policy and good medical practice, acute medical care will be provided to subjects for any immediate allergic reactions or other injury resulting from participation in this research study.

4.2.5 7-Day Solicited Reactogenicity and Follow-up

Subjects will be given a “Diary Card” to use as a memory aid, on which to record temperature and symptoms daily for 7 days after each injection. Subjects will be trained and encouraged to use the secure electronic database but will have the option to complete a paper diary card. When the diary card parameters are recorded directly by the subject in the electronic database, the subject’s electronic record will be the source for these data. When collected on paper, the paper diary card will be used as a source document. When neither paper nor electronic diary is available from the subject, the study clinician will document the source of reactogenicity information recorded in the study database.

The solicited signs and symptoms on the diary card will include the following parameters: unusually tired/feeling unwell, muscles aches (other than at injection site), headache, chills, nausea, joint pain, and pain/tenderness at injection site. Subjects will also record the day’s highest measured temperature and measurement of largest diameter for redness and swelling at injection site.

Follow-up on subject well-being will be performed by telephone on the first day following all injections and by clinic visits as shown in the Schedule of Evaluations (Appendix II)

Events following any study injection that may require clinical evaluation include rash, urticaria, fever of 38.5°C (Grade 2) or higher lasting greater than 24 hours, or significant impairment in the activities of daily living. Additionally, other clinical concerns may prompt a study visit based on the judgment of a study clinician.

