5. SAFETY AND ADVERSE EVENT REPORTING

5.1 ADVERSE EVENTS

An adverse event (AE) is any untoward or unfavorable medical occurrence in a human subject, including any abnormal sign (e.g., abnormal physical exam or laboratory finding), symptom, or disease temporally associated with the use of study treatment, whether or not considered related to the study treatment.

Each AE will be graded according to the Table for Grading Severity of Adverse Events (Appendix III). The following guidelines will be used to determine whether or not an AE is recorded in the study database:

- Solicited AEs (i.e., reactogenicity parameters) will be recorded by the subject in paper or electronic diary cards for 7 days after each injection. If paper diary card is completed by subject, data will be transcribed by clinician into the study database without attribution assessments. Clinicians will follow and collect resolution information for any reactogenicity symptoms that are not resolved within 7 days.
- All unsolicited AEs will be recorded in the study database from receipt of first study injection through the “Week 4” visit after each study injection with attribution assessments. At other time periods between injections and when greater than 4 weeks after the booster injection, only SAEs (Section 5.2), new chronic medical conditions, and influenza or influenza-like illness (ILI) will be recorded through the last study visit.
- Cases of influenza or influenza-like illness will be evaluated using clinical judgment and current CDC definition of influenza symptoms (<https://www.cdc.gov/flu/about/disease/complications.htm>) and recorded on a case report form rather than on an AE form. ILI is defined as fever (temperature of 100F [37.8C] or greater) and a cough and/or sore throat in the absence of a known cause other than influenza.

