6.3 ENDPOINTS

6.3.1 Primary Endpoints: Safety

Assessment of product safety will include clinical observation and monitoring of hematological and chemical parameters. Reactogenicity will be closely monitored for 7 days after each injection and safety evaluated by clinical visits throughout 40 weeks. See Section 4.2 and Appendix II for details and specified time points.

The following parameters will be assessed for all study groups:

- Occurrence of solicited local reactogenicity symptoms for 7 days following each injection
- Occurrence of solicited systemic reactogenicity symptoms for 7 days following each injection
- Change from baseline in safety laboratory measures
- Occurrence of AEs of all severities through the “Week 4” visit after each injection
- Occurrence at any time throughout the study of SAEs or new chronic medical conditions that require ongoing medical management.

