6.5.3 Safety Analysis

6.5.3.1 Reactogenicity

The number and percentage of participants experiencing each type of reactogenicity sign or symptom will be tabulated by severity. For a given sign or symptom, each participant's reactogenicity will be counted once under the maximum severity for all assessments.

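### Solicited systemic symptoms have no graded pre-injection record; adding one on Day 0 and at Week 16 is a cheap improvement to the reactogenicity table

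*Combined protocol and SAP*

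**What the plan says.** Section 6.3.1 lists among the primary endpoints "Occurrence of solicited systemic reactogenicity symptoms for 7 days following each injection", with a parallel endpoint for local symptoms. The diary in Section 4.2.5 asks about tiredness or feeling unwell, muscle aches, "headache, chills, nausea, joint pain, and pain/tenderness at injection site", plus highest temperature and the diameter of redness and swelling. It is a card "on which to record temperature and symptoms daily for 7 days after each injection".

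For the state before injection, Section 4.2.3 says: "Day 0 evaluations and medical history prior to the first injection are the baseline for subsequent safety assessments". Footnote 1 to the Appendix II schedules repeats this for adverse events. Section 4.2.4 adds: "On the injection day (prior to injection), study subjects will be clinically evaluated". It allows rescheduling when fever or acute illness precludes vaccination. The Group 2 schedule in Appendix II marks interim history and vital signs, which include temperature, at both injection visits.

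On handling of the diary data, Section 5.1 says that for paper cards "data will be transcribed by clinician into the study database without attribution assessments". Nothing in the plan gives electronic entries an attribution either. Under Section 6.5.3.1, a participant's reactogenicity for a given symptom "will be counted once under the maximum severity for all assessments". Sections 4.2.5 and 6.5.3.1 do not mention a comparison with the pre-injection state.

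**The concern.** A symptom that predates the injection can usually be separated from one that follows it in three ways: an untreated group, an attribution judgement, or a baseline record of the same item. Here every group receives active product and diary entries are not attributed. The baseline is general rather than item by item, and the table does not use it. A subject who arrives with a mild headache or aching joints, not ill enough to be rescheduled, and who still has the symptom that evening, is counted in the systemic reactogenicity percentage.

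At stake are the absolute systemic rates per group. These are a main product of a first-in-human trial and are what a reader will carry forward to later trials. The dose comparison (Group 1 then Group 2, enrolled in sequence) and the age comparisons (3A with 3B, 4A with 4B) are not randomized. They inherit the excess unequally if ongoing symptoms are more common in one group. The boost is the weaker spot, because the only named baseline precedes the first injection, about 16 weeks earlier.

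**Working it through.** **1. The plan's own figures.** None rests on this point. The exact upper limits for zero events reproduce: 1 − 0.025^(1/5) = 0.522 and 1 − 0.025^(1/10) = 0.308, as in Table 6-2. They are unchanged by anything below.

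**2. Following one subject through the text.** Take a mild joint ache present on the morning of injection and for two days after.
- Section 4.2.4: a clinical evaluation takes place. The ache does not preclude vaccination, so the subject proceeds.
- Section 4.2.3 and Appendix II: the ache may appear in the history. No graded entry on the diary items is described.
- Section 4.2.5: the diary starts after injection, and the ache is recorded.
- Section 5.1: no attribution is made.
- Section 6.5.3.1: the subject counts once for joint pain, at maximum severity.

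At Week 16 the path is the same, except that the named baseline is the Day 0 one.

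**3. What one subject is worth.** Planned sizes are 5 (Groups 1 and 2), 10 (each age cohort in Part II) and 20 (each Part II regimen). One subject is 1/5 = 20 points, 1/10 = 10 points and 1/20 = 5 points.

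**4. Illustration under an assumed prevalence.** The documents give no prevalence for symptoms ongoing at injection. Let b be the share of subjects with a given symptom ongoing, who then record it. The expected number of carry-over subjects is n × b, and the chance of at least one is 1 − (1 − b)^n.

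| b (assumed) | n=5: expected | n=5: at least one | n=10: expected | n=10: at least one |
|---|---|---|---|---|
| 5% | 0.25 | 23% | 0.5 | 40% |
| 10% | 0.5 | 41% | 1 | 65% |
| 20% | 1 | 67% | 2 | 89% |

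**5. Why these are upper limits.** A subject who would have reported the symptom after injection anyway adds nothing to the any-grade count. If a share v would have done so independently, the net excess is n × b × (1 − v). With v = 30% (also assumed), the n=10 range becomes 10 × 0.05 × 0.7 = 0.35 to 10 × 0.20 × 0.7 = 1.4. The tabulated rate is 1 − (1 − b)(1 − v). For b = 5%, 10% and 20% this is 33.5%, 37% and 44%, against a true 30%.

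**6. Against sampling error.** Table 6-2 gives 0.003 to 0.445 for 1/10. An excess of this size lies well inside the uncertainty of a single group. Unlike sampling error, it pushes the rate in one direction only.

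**The case against.** The strongest reply is that the plan does look at subjects before injection, enrolls people in good general health, and can reschedule those with fever or acute illness. That stands. It also narrows the point in several ways.

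- **Local symptoms.** A reader might infer that both solicited primary endpoints are affected. The local items are tied to the injection site, and Section 4.2.4 has clinicians consider arm injuries and skin problems when choosing the arm. Little can carry over, so the point is limited to systemic symptoms. Among these, the tiredness item is already worded relative to the subject's usual state. Temperature is a diary item that is taken at injection visits.
- **Causal labels.** A reader might infer that the plan classes pre-existing symptoms as vaccine reactions. It does not. The endpoint is occurrence, and Section 6.5.3.1 tabulates by severity only. The issue is what the percentages include, not a label attached to them.
- **Decisions.** None of the three pause criteria in Section 4.5.1 counts non-serious solicited symptoms. Under Section 4.4.1, self-limited Grade 3 reactogenicity does not require discontinuation. Dose escalation in Section 4.3 is a judgement on five subjects with no symptom-rate threshold. The bias overstates reactogenicity; it does not hide harm.
- **Randomization.** Group 3 and Group 4 are randomized within age strata, so ongoing symptoms are balanced in expectation at the prime.
- **Silence.** The diary card and case report forms are not among the documents. An item-level pre-dose entry may exist there, but the plan describes none.

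What survives is that a general evaluation is not a graded record of the same items, and the table has no rule that would use one.

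**Conclusion.** This is a cheap improvement, not an error in the plan. The solicited systemic percentages will include mild symptoms already present at injection, and the plan as written offers no way to separate them. The effect is upward on per-group absolute rates. It can also distort the non-randomized dose and age comparisons if ongoing symptoms differ between groups.

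The magnitude cannot be derived from the documents. The only part free of assumptions is the weight of one subject. The expected counts rest on an assumed prevalence of 5% to 20% per symptom and on each such subject recording the symptom after injection, so they are ceilings.

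A reader might go further and conclude that the stated Day 0 baseline cannot be applied at all, or that a pre-dose record would make up for the missing placebo group. The documents do not support the first: history, examination and temperature are available, though not item by item or graded. The second does not follow, because symptoms that arise by chance during the 7 days would still be counted.

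**What to change.** On Day 0 and, for Groups 2 to 4, at Week 16, have the subject complete one pre-injection line on the diary or case report form. It should carry the same six systemic items and the same grades. State in Section 4.2.5 that this line is the symptom baseline for that injection.

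In Section 6.5.3.1, keep the raw count at maximum severity, so that results stay comparable with other trials. Add a column for symptoms that are new, or worse in grade, relative to the pre-injection record of the same injection.

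The cost is a few minutes at visits that already take place, one form line and one table column. No visit, sample size or pause rule changes. The limitation to state alongside the table is that a single reading removes ongoing symptoms only. The record has to be taken at the time, since it cannot be reconstructed reliably afterwards.
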